9.1.4 Progression-Free Survival

Progression-Free Survival (PFS) is defined as the duration of time from registration to time of documented disease progression (radiographic or clinical) or death without documentation of disease progression. Patients who are alive and without evidence of progression will be censored at the date of last disease evaluation.

9.2 Other Response Parameters

9.2.1 Time to PSA Progression

PSA progression will be defined according to the consensus guidelines of PCWG2¹⁵. For patients with PSA declines at Week 13, the PSA progression date is defined as the date that a $\geq 25\%$ increase and an absolute increase of ≥ 2 ng/mL above the nadir is documented, which is confirmed by a second consecutive value 3 or more weeks later. For patients with no PSA decline at Week 13, the PSA progression date is defined as the date that a $\geq 25\%$ increase and an absolute increase of ≥ 2 ng/mL above the baseline is documented, which is confirmed by a second consecutive value 3 or more weeks later.

9.2.2 Overall survival

The duration of overall survival will be calculated for all patients from the date of registration until the date of death due to any cause.

10.2.3 PSA Response

PSA responses will be evaluated according to the criteria defined by the PCWG2¹⁵.

11.0 ADVERSE EVENTS

11.1 Adverse Event Definitions

An adverse event (AE) is any untoward medical occurrence associated with the use of a drug in humans, whether or not considered drug related. An adverse event can be any unfavorable and unintended sign (eg, including an abnormal laboratory finding), symptom, or disease temporally associated with the use of the drug, without any judgment about causality. This includes any newly occurring event or previous condition that has increased in severity or frequency since the administration of drug.

An adverse event is considered a **serious adverse event** (SAE) if it results in any of the following outcomes:

- 1) Results in death
- 2) Is a life-threatening (ie, its occurrence places the patient or subject at immediate risk of death)
- 3) Requires inpatient hospitalization or prolongation of existing hospitalization for ≥ 24 hours
- 4) Results in a persistent or significant incapacity or substantial disruption of the ability to conduct normal life functions
- 5) Is a congenital anomaly/birth defect
- 6) Is an important medical event that may not result in death, be life threatening, or require

hospitalization but may be considered serious when, based upon medical judgment, may jeopardize the patient or subject and may require medical or surgical intervention to prevent one of the outcomes listed in this definition.

7) Results in cancer

Suspected Adverse Event

Suspected adverse reaction means any adverse event for which there is a reasonable possibility that the drug caused the adverse event. For the purposes of IND safety reporting, 'reasonable possibility' means there is evidence to suggest a causal relationship between the drug and the adverse event. A suspected adverse reaction implies a lesser degree of certainty about causality than adverse reaction, which means any adverse event caused by a drug.

Unexpected Adverse Events

An adverse event is considered "unexpected" if it is not listed in the Investigator Brochure or is not listed at the specificity or severity that has been observed; or, if an Investigator Brochure is not required or available, is not consistent with the risk information described in the general investigational plan or elsewhere in the current application.

11.2 Adverse Event Characteristics

CTCAE term (AE description) and grade: The descriptions and grading scales found in the revised NCI Common Terminology Criteria for Adverse Events (CTCAE) version 4.0 (Appendix D) will be utilized for AE reporting. If specific grading is not available in the CTCAE for a particular AE's severity/intensity, the Investigator is to revert to the general definitions of Grade 1 through 5 and use his/her best medical judgment. The 5 general grades are: Grade 1 = mild, Grade 2 = moderate, Grade 3 = severe, Grade 4 = life-threatening or disabling, Grade 5 = death related to AE.

Attribution of the AE:

Investigators are required to assess whether there is a reasonable possibility that tivozanib hydrochloride caused or contributed to the adverse event. The following general guidance may be used.

- Definite The AE *is clearly related* to the study treatment.
- Probable The AE *is likely related* to the study treatment.
- Possible The AE *may be related* to the study treatment.
- Unlikely The AE *is doubtfully related* to the study treatment.
- Unrelated The AE is clearly NOT related to the study treatment.

11.3 Procedures for Reporting AEs and SAEs

Adverse events, both serious and non-serious, and deaths that occur during the patient's study participation (from time of written informed consent through 30 days after receiving the last dose of tivozanib hydrochloride) will be documented. All subjects receiving at least 1 dose of tivozanib hydrochloride, whether completing the treatment period or not, should be followed for

30 days after the last dose of tivozanib hydrochloride. New AEs and changes in ongoing AEs or those with an unknown outcome must be followed for 30 days after the last dose of tivozanib hydrochloride. All SAEs should be monitored until they are resolved or are clearly determined to be due to a patient's stable or chronic condition or intercurrent illness(es). The Investigator will determine the seriousness, intensity, and causality of an adverse event associated with the use of the study drug (ie, events where there is a reasonable possibility that the event may have been caused by the study drug).

All SAEs should be recorded on a Medwatch Form 3500A and sent to the FDA, to AVEO Pharmacovigilance/Drug Safety, National Comprehensive Cancer Network (NCCN), and to the Principal Investigator/Study Coordination Center (if applicable).

SAE Reporting Contact Information

Food and Drug Administration Center for Drug Evaluation and Research Division of Oncology Products [name]

SAE Reporting Contact Information

Please submit SAE Reports to Parexel GPPG via email ([contact]). If submission via email is not possible or delayed then submission via fax (NA [contact]) is acceptable.

Pharmacovigilance/Drug Safety AVEO Pharmaceuticals, Inc [name] [contact]

E-mail: [contact]

SAE Reporting Contact Information

National Comprehensive Cancer Network (NCCN) [contact] Email: [contact]

SAE Reporting Contact Information

[name]/Massachusetts General Hospital Cancer Center [contact] [contact] Email: [contact]

Medwatch 3500A Reporting Guidelines:

In addition to completing appropriate demographic and suspect medication information, the report should include the following information within the Event Description (Section 5) of the Medwatch Form 3500A (Appendix E):

- Treatment regimen (dosing, frequency, combination therapy)
- Protocol description (include number if assigned)
- Description of event, severity, treatment, and outcome, if known
- Supportive diagnostic and laboratory results
- Investigator's assessment of the relationship of the SAE to each investigational product and suspect medication

Follow-up information

Additional information may be added to a previously submitted report by any of the following methods:

- Adding to the original Medwatch Form 3500A and submitting it as follow-up
- Adding supplementary summary information and submitting it as follow-up with the original Medwatch Form 3500A
- Summarizing new information and faxing it with a cover letter including subject identifiers (ie, DOB, initials, subject number), protocol description and number, suspect drug, brief adverse event description, and notation that additional or follow-up information is being submitted

Occasionally, AVEO Pharmacovigilance/Drug Safety may contact the reporter for additional information, clarification, or current status of the subject for whom the adverse event was reported.

11.4 Safety Reporting Requirements for IND Holders

For Investigator Sponsored IND Studies there are additional reporting requirements for the FDA in accordance with the guidance set forth in 21 CFR 312.32. Sponsor-investigators of studies conducted under an IND must comply with the following safety reporting requirements:

1. Expedited IND Safety Reports

The Sponsor-Investigator is required to report all serious, unexpected and related adverse events directly to the FDA on a MEDWATCH Form 3500A (Appendix E) within 7 (if fatal or life-threatening) or 15 calendar days of first awareness, as described below.

AVEO Pharmacovigilance/Drug Safety and NCCN must be informed of ALL SAEs (final report) on a MEDWATCH Form 3500A within 15 days of first awareness, whether or not they are considered related to the investigational agent(s)/protocol intervention(s).

Reporting to the FDA

The Sponsor-Investigator must report in an IND safety report any suspected adverse reaction that is both serious and unexpected (21 CFR 312.32). Before submitting this report, the sponsor needs to ensure that the event meets all three of the definitions contained in the requirement:

- Suspected adverse reaction
- Serious
- Unexpected

If the adverse event does not meet all three of the definitions, it should not be submitted as an expedited IND safety report to the FDA.

The timeframe for submitting an IND safety report to FDA and all participating investigators is no later than 15 calendar days after the investigator determines that the suspected adverse event or other information qualifies for reporting.

Any fatal or life-threatening serious, unexpected and related adverse event must be reported to FDA no later than 7 calendar days after initial awareness. Sponsor-Investigators should initially notify FDA by telephone or facsimile transmission. Other means of rapid communication (e.g., email) may also be used, if prior to transmission, the Project Manager in the FDA review division that has responsibility for review of the IND confirms that other means of rapid transmission are acceptable.

Any serious, unexpected and related adverse event that is not fatal or life-threatening must be reported to FDA no later than 15 calendar days after initial awareness.

Reporting to AVEO Pharmacovigilance/Drug Safety and NCCN

AVEO Pharmacovigilance/Drug Safety and NCCN must be informed of **ALL** SAE/suspected unexpected serious adverse reaction (SUSAR) final reports within 15 days of first awareness.

The Sponsor-Investigator must comply with any applicable requirements related to the reporting of SAEs involving his/her subjects to the IRB that approved the study.

2. IND Annual Reports

In accordance with the regulation 21 CFR 312.33, the Sponsor-Investigator shall within 60 days of the anniversary date that the IND went into effect submit a brief report of the progress of the investigation. Please refer to Code of Federal Regulations, 21 CFR 312.33 for a list of the elements required for the annual report. All IND annual reports submitted to the FDA by the Sponsor-Investigator should be copied to AVEO. Copies of such reports should be submitted to AVEO via NCCN.

11.5 Procedures for Reporting Subject Death

Any death experienced by a subject after enrollment through 30 days of receiving the last dose of tivozanib hydrochloride, regardless of relationship to study drug, or any death that occurs more than 30 days after receiving study drug that is believed to be study drug-related must be promptly reported (within 24 hours of the investigator becoming aware of the event) by telephone, telefax, or e-mail transmission to AVEO Pharmacovigilance/Drug Safety and NCCN. Reports of all onstudy deaths must also be communicated promptly to the FDA and the appropriate Institutional Review Board (IRB) and/or reported in accordance with local law and regulations.

11.6 Procedures for Reporting Study Drug Overdose

An overdose of tivozanib hydrochloride should be reported if the dose of tivozanib hydrochloride administered is greater than the assigned dose for the subject.

Should a subject experience an overdose during the course of the study (whether symptomatic or not, and regardless of seriousness), the Sponsor-Investigator or qualified designee must complete a Medwatch Form 3500A to report the overdose to AVEO Pharmacovigilance/Drug Safety and NCCN within 24 hours of first becoming aware of the overdose. Follow-up information on the outcome of the overdose should be forwarded to the AVEO Pharmacovigilance/Drug Safety and NCCN.

Any event associated with, or observed in conjunction with, a product overdose (whether accidental or intentional) or a product abuse and/or withdrawal is considered an AE and should be reported as such. If a SAE occurs in conjunction with the overdose, then the reporting time frame for a SAE should be followed.

11.7 Procedures for Reporting Drug Exposure During Pregnancy and Birth Events

All pregnancies, including pregnancies in female partners of male study participants, occurring from the date of ICF signature until 45 days following tivozanib hydrochloride administration must be documented. If it is confirmed that a study participant has become pregnant while participating in this trial, study drug administration will be discontinued immediately. Any pregnancy occurring during this study will be reported immediately to AVEO Pharmacovigilance/Drug Safety and NCCN.

The Sponsor-Investigator must actively follow-up, document and report the outcome of any pregnancy even if the subject has withdrawn from the study. The Sponsor-Investigator will then report follow-up information to AVEO Pharmacovigilance/Drug Safety and NCCN regarding the course of the pregnancy, including perinatal and neonatal outcome. Timelines vary according to the nature of the pregnancy outcome:

- For normal outcomes, AVEO Pharmacovigilance/Drug Safety should be notified within 45 days from birth/delivery.
- For abnormal outcomes, the fully completed Medwatch Form 3500A must be sent to AVEO Pharmacovigilance/Drug Safety according to the same procedures and timelines described for expedited AE reporting.

For questions related to safety reporting, contact: AVEO Pharmacovigilance/Drug Safety.

12. DATA AND SAFETY MONITORING

12.1 Data Reporting

The QACT will collect, manage, and monitor data for this study. The schedule for completion and submission of case report forms (paper or electronic) to the QACT is as follows:

| Form | Submission Timeline |
|------------------------------|--|
| Eligibility Checklist | Complete prior to registration with QACT |
| On Study Form | Within 14 days of registration |
| Baseline Assessment Form | Within 14 days of registration |
| Treatment Form | Within 10 days of the last day of the cycle |
| Adverse Event Report Form | Within 10 days of the last day of the cycle |
| Response Assessment Form | Within 10 days of the completion of the cycle required for response evaluation |
| Off Treatment/Off Study Form | Within 14 days of completing treatment or being taken off study for any reason |
| Follow up/Survival Form | Within 14 days of the protocol defined follow up visit date or call |

12.2 Safety Monitoring

The DF/HCC Data and Safety Monitoring Committee (DSMC) will review and monitor toxicity and accrual data from this trial. The committee is composed of clinical specialists with experience in oncology and who have no direct relationship with the study. Information that raises any questions about participant safety will be addressed with the Principal Investigator and study team.

The DSMC will meet quarterly and/or more often if required to review toxicity and accrual data. Information to be provided to the committee may include: up-to-date participant accrual; current dose level information; DLT information; all grade 2 or higher unexpected adverse events that have been reported; summary of all deaths occurring within 30 days for Phase I or II protocols; any response information; audit results, and a summary provided by the study team. Other information (e.g. scans, laboratory values) will be provided upon request.

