|-----------------------------------|--------------------|--------------------------------|
| | (N=785) | (N=259) |
| Preferred Term | n (%) | n (%) |
| Any Adverse Event | 681 (86.8) | 235 (90.7) |
| Hypertension | 333 (42.4) | 113 (43.6) |
| Dysphonia | 176 (22.4) | 55 (21.2) |
| Fatigue | 173 (22.0) | 50 (19.3) |
| Diarrhea | 168 (21.4) | 59 (22.8) |
| Asthenia | 123 (15.7) | 40 (15.4) |
| Dyspnea | 111 (14.1) | 29 (11.2) |
| Back pain | 101 (12.9) | 35 (13.5) |
| Nausea | 99 (12.6) | 31 (12.0) |
| Decreased appetite | 89 (11.3) | 27 (10.4) |
| Cough | 85 (10.8) | 20 (7.7) |
| Palmar-plantar erythrodysesthesia | 82 (10.4) | 36 (13.9) |
| Weight decreased | 79 (10.1) | 47 (18.1) |

Pooled data from 4 core RCC monotherapy studies AV-951-07-201, AV-951-10-202, AV-951-09-902, and AV-951-09-301. From Tivozanib Hydrochloride Investigator Brochure, version 9.2, May 2012.

The incidence of hypertension and palmar-plantar erythrodysesthesia syndrome presented in this table include events of all grades. For the purposes of regulatory reporting, these events are considered expected at \leq CTCAE Grade 3. Higher grades are considered unexpected.

In other monotherapy studies AV-951-10-112, KRN951/03-B01, and AV-951-08-105, TEAEs were reported in 106 of the 109 subjects (47/50 [94.0%], 42/42 [100%], and 17/17 [100%], respectively). In general, the most frequently reported TEAEs in tivozanib hydrochloride-treated subjects across these 3 studies were hypertension (range of 41.2% to 59.5%), fatigue (26.0% to 76.5%), diarrhea (10.0% to 54.8%), nausea (16.0% to 52.9%), and headache (20.0% to 38.1%). The lowest incidence of TEAEs was observed in Study AV-951-10-112, in which subjects were administered tivozanib hydrochloride for only 3 weeks. Despite differences in dosing duration, and other factors such as underlying disease, dosing schedule, and the small number of subjects in each study, the TEAE patterns are generally consistent with those seen in the 4 core monotherapy studies.

When tivozanib hydrochloride is administered in combination with 1 or more approved antineoplastic agents, the expectedness determination should take into account the labeling of each specific marketed drug taken in combination based upon reference documents which will be included or referenced in the clinical study protocol. The labeled events should, in general, be

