considered expected for at least one of the drugs in the combination. The contribution of tivozanib to the severity or frequency of the events is currently unknown.

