5. TREATMENT PLAN

Treatment will be administered on an outpatient basis. Expected toxicities and potential risks as well as dose modifications are described in Section 6 (Expected Toxicities and Dosing Delays/Dose Modification).

The treatment plan is outlined in the table below. Tivozanib will be taken orally once daily for 3 out of 4 weeks on a continuous basis. Enzalutamide will be taken orally once daily without any scheduled interruptions, on a continuous basis.

| Treatment Description | | | | | | |
|-----------------------|-------------|--------|---------------|------------|-----------------|--|
| Agent | Precautions | Dose | Route | Schedule | Cycle Length | |
| Tivozanib | None | 1.5 mg | PO once daily | Weeks 1-3 | | |
| Enzalutamide | None | 160 mg | PO once daily | Continuous | 28 days | |

Because this combination has not been previously tested, a safety run-in will be conducted at the outset of the trial. After the first 3 patients are enrolled, accrual will be held until all three patients complete the first 1 month of treatment. Additionally, after a total of 10 patients are enrolled, these patients will be analyzed for safety and toxicity by the DSMC. If any treatment-related, expected or unexpected grade 3 or higher adverse events occur during the first month of treatment in the first 3 patients, or if the rate is >30% among the first 10 patients during the first month of treatment, further accrual will be halted for reconsideration of the appropriateness of the dosing schedules.

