14. STATISTICAL CONSIDERATIONS

14.1. Study Design/Endpoints

The phase 2 study will evaluate the efficacy of enzalutamide and tivozanib in patients with mCRPC. The primary endpoint will be progression free survival (PFS), defined as the time from registration to the earlier of progression (radiographic or clinical) or death and, if censored, the date of last disease evaluation. Based on phase 3 data, the median PFS with enzalutamide alone in chemotherapy naive mCRPC is 14 months. The hypothesis is that the addition of tivozanib will significantly enhance efficacy. An improvement of 60% to a median PFS of 22.4 months will be considered worthy of further study. Assuming exponential distribution, this implies a hazard ratio (HR) of 0.625 relative to historical control (hazard rate from 0.0495 to 0.0309). Using a one-sample exponential test, there will be 80% power to demonstrate a 60% improvement at a one-sided Type 1 error rate of 10% with enrollment of 38 patients and 20 PFS events.

Because this combination has not been previously tested, a safety run-in will be conducted at the outset of the trial. After the first 3 patients are enrolled, accrual will be held until all three patients complete the first 1 month of treatment. Additionally, after a total of 10 patients are enrolled, these patients will be analyzed for safety and toxicity by the DSMC. If any treatment-related, expected or unexpected grade 3 or higher adverse events occur during the first month of treatment in the first 3 patients, or if the rate is >30% among the first 10 patients during the first month of treatment, further accrual will be halted for reconsideration of the appropriateness of the dosing schedules.

The table below gives the probability of observing 1 or more toxicities among the first 3 patients or 3 or more among the first 10 patients given different true underlying toxicity rates.

| True toxicity rate | 1% | 10% | 20% | 30% | 40% | 50% |
|--|--------|-------|-------|-------|-------|-------|
| Probability of Stopping Early (≥ 1/3) | 0.030 | 0.271 | 0.488 | 0.657 | 0.784 | 0.875 |
| Probability of Stopping Early (≥ 3/10) | <0.001 | 0.070 | 0.322 | 0.617 | 0.832 | 0.945 |

Thus, if the true underlying proportion of toxic events is 30% at the current dosing schedules, there is a greater than 60% chance of stopping early.

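### Section 12.2 does not ensure that the DSMC receives the expected grade 3 events its 10-man rule counts, and that review is tied to enrolment of the 10th man rather than to completed first-month data

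*Combined protocol and SAP*

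**What the plan says.** **The rule.** Sections 1.1, 5 and 14.1 set a run-in rule that makes no distinction by expectedness. It has two triggers, and either one stops recruitment so that the dosing schedules can be looked at again. The trigger for the opening three men reads: "If any treatment-related, expected or unexpected grade 3 or higher adverse events occur during the first month of treatment in the first 3 patients". The second trigger applies the same kind of event to the opening ten men and is met when more than 30% of them are affected in month 1.

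**Who applies it at 10.** Sections 5 and 14.1 give this to the DSMC: "after a total of 10 patients are enrolled, these patients will be analyzed for safety and toxicity by the DSMC".

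**What the committee receives.** Section 12.2 describes information that may be supplied. Its one adverse event listing is "all grade 2 or higher unexpected adverse events that have been reported". It also names accrual, dose level and DLT information, 30-day deaths, response information, audit results and a study-team summary, with other information on request.

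**What is expected.** Section 2.1.1.3 treats hypertension and palmar-plantar erythrodysesthesia, for regulatory reporting, as expected up to and including Grade 3: "Higher grades are considered unexpected". For combinations with marketed drugs, labelled events are in general to be "considered expected for at least one of the drugs in the combination".

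**Timing.** Section 12.2: "The DSMC will meet quarterly and/or more often if required to review toxicity and accrual data". Sections 5 and 14.1 state a hold at three men ("After the first 3 patients are enrolled, accrual will be held until all three patients complete the first 1 month of treatment") and none at 10. Section 1.1 instead caps enrolment at 10 while the first three complete their month.

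**The concern.** The rule deliberately includes expected events, while the one listing the committee is told it may receive excludes them. The combination is untested, and Section 2.1.1.3 concedes that tivozanib's contribution to the severity or frequency of events in combination is unknown. A known toxicity occurring at grade 3 more often than anticipated is therefore something the run-in should be able to detect. Expected grade 3 events are foreseeable: hypertension is tivozanib's most frequent event, and Section 6.2.1 counts worsening of baseline-controlled hypertension that needs more intensive therapy as Grade 3. The same listing serves the DSMC's quarterly monitoring for the rest of the trial, so the gap would outlast the run-in.

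The second issue is the trigger. The rule needs a month of data on each of 10 men, but the review is keyed to the 10th enrolment, when his month has only begun. If accrual continues while his data mature and the committee waits for a scheduled meeting, more men are exposed before the rule is applied to the full 10.

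**Working it through.** **1. The plan's own table.** With true rate p, P(at least 1 of 3) = 1 − (1 − p)³; at p = 0.30 this is 1 − 0.343 = 0.657. P(at least 3 of 10) is the binomial upper tail: 0.617 at p = 0.30 and 0.833 at p = 0.40 (plan: 0.832). All six columns of both rows agree within 0.001. These figures assume that every qualifying event is counted, expected or not.

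**2. Rule against listing.**

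| Event in month 1 | Counted by the rule? | In the Section 12.2 adverse event listing? |
|---|---|---|
| Unexpected, related, grade 3+ | Yes | Yes |
| Hypertension above Grade 3, related | Yes | Yes (unexpected by Section 2.1.1.3) |
| Hypertension at Grade 3, related | Yes | No, if the Section 2.1.1.3 classification is used |
| Labelled enzalutamide event at grade 3 within its listed severity, related | Yes | No, where classed as expected |

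The other items do not clearly close the gap. DLT is defined nowhere in the protocol, and there is no dose-escalation scheme to give dose level a meaning. Deaths cover fatal events only. The content of the study-team summary is unspecified, and data on request depend on someone asking.

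**3. Illustration of what could be lost.** The documents do not give the share f of men with a qualifying event whose events are all expected. I assume 0 to 75%, and that the committee sees nothing beyond the listing, which is a worst case. The visible rate is p(1 − f). At p = 0.40:

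| f | Visible rate | P(≥3 of 10) | P(≥4 of 10) |
|---|---|---|---|
| 0 | 0.40 | 0.833 | 0.618 |
| 25% | 0.30 | 0.617 | 0.350 |
| 50% | 0.20 | 0.322 | 0.121 |
| 75% | 0.10 | 0.070 | 0.013 |

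Both thresholds are shown because the plan's table uses 3 of 10, whereas its text requires a rate above 30%, which means 4 of 10. That discrepancy is a separate matter.

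**4. Timing.** Inputs: 2 patients a month (Section 14.2), a 28-day cycle (Section 5), the adverse event form due 10 days after cycle end (Section 12.1), and quarterly meetings (Section 12.2).

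- 10th man's month only: 28/30.4 = 0.92 months × 2 = 1.8 further men.
- To his form deadline: (28 + 10)/30.4 = 1.25 months × 2 = 2.5 further men.
- Plus a full quarter's wait: 1.25 + 3 = 4.25 months × 2 = 8.5 further men, about 18 of 42 enrolled.

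**5. Could a halt come sooner?** At 2 a month, entries are half a month apart, so the 8th man enters one month before the 10th. About 8 of the 10 have then finished month 1 when the 10th enrols. Four affected among them already gives 4/10 = 40%, above the threshold. The figures in step 4 therefore apply only if the outcome depends on the last men or the halt waits for the formal review.

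**The case against.** The strongest reply is that Section 12.2 is a generic, permissive list, not a filter. It opens by giving the committee toxicity data without limiting them by expectedness, and allows other information on request. Sections 5 and 14.1 separately require a DSMC analysis of these 10 men, beside a rule that names expected events, and that specific mandate could be said to govern. The data exist on the per-cycle forms. All of this stands. A reader might infer that the committee will see only unexpected events and cannot apply the rule; the documents do not support that.

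Nor is worsening severity removed wholesale. Under Sections 2.1.1.3 and 11.1, an event beyond its listed severity is unexpected and so falls in the listing. What can drop out is an expected event at grade 3 within its listed severity, and any excess frequency of such events. The Section 2.1.1.3 cut-off is also stated for regulatory reporting, not for DSMC review.

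It is tempting to size the gap from tivozanib's hypertension rate (42.4% in the pooled renal studies). That rate covers all grades in another disease, and no grade 3+ rate is given, so it does not measure the events at issue.

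On timing, a reader might infer that the rule cannot act until 12 to 18 men are enrolled. The halt is not reserved to a DSMC meeting, meetings may be more frequent than quarterly, and the threshold may be crossed early.

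The DSMC is also not the only safety recipient. Section 11.3 sends all SAEs to the FDA, the manufacturer, NCCN and the Principal Investigator or coordinating centre. But grade 3 hypertension managed without admission need not be an SAE, and the DSMC is not among those recipients.

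**Conclusion.** The point holds as a gap in what is guaranteed, not as proof that a signal would be missed. The rule counts expected grade 3+ events, the only adverse event listing for the committee applying it leaves them out, and nothing requires that they be supplied. The listing could therefore omit events needed for the 10-man rule and for later monitoring. How much detection would suffer is unknown: the fall from 0.833 to 0.322 at a 40% true rate (threshold 3 of 10) assumes that half the affected men have only expected events and that the committee sees nothing else.

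The trigger is also incomplete. About 2.5 further men enrol if a halt waits for the 10th man's Cycle 1 form, and up to about 8.5 if review then waits a full quarter. This is a conditional range that assumes steady accrual at the planned rate and no hold at 10.

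The change should be made: it concerns safety oversight of an untested combination and uses data already collected. The documents do not say whether the run-in is finished; if it is, the Section 12.2 correction still matters for ongoing monitoring.

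**What to change.** - **Section 12.2:** replace the adverse event item with all grade 3 or higher events regardless of expectedness, plus all grade 2 unexpected events. Define DLT and dose level for this trial, or delete them.
- **Sections 5 and 14.1:** state that the 10-man review uses completed first-month data on all 10 men, and is an ad hoc DSMC review held when the 10th man's Cycle 1 adverse event form is due, not left to the next quarterly meeting.
- **Sections 1.1, 5 and 14.1:** reconcile enrolment during the run-in. Section 1.1 allows up to 10 men while the first three complete their month; Sections 5 and 14.1 hold accrual at three. State also whether accrual is held at 10. If it is not, the 2.5 further men in the working remain even with a prompt ad hoc review.

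**Cost:** a wording amendment, one ad hoc review (which Section 12.2 already permits) and slightly longer DSMC listings. No new data are collected, since Section 12.1 already requires the per-cycle forms.
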